[figure not shown]
Official Title: The Impact of Brief One-time Education and Coach Encouragement on Hydration Status in Child Judo Athletes

NCT number: E.912346

Date of the document: 22nd of May 2025

Study Design

This within-subject experimental study examined the effects of coach encouragement and a brief one-time educational intervention (hereinafter referred to as education) on the hydration status of child judo athletes, compared to a no-intervention control, during a four-day training camp. As a within-subject design was adopted, each participant underwent all experimental conditions across different days. Athletes were unaware of the intervention conditions assigned to each day, and the educational session was presented without emphasizing its experimental nature. The order of conditions was fixed (control first, then coach encouragement, and finally education) to minimize potential carryover effects. The researcher conducting the hydration assessments was not blinded. Athletes and their legal guardians were informed about the nature of the study, and written consent was obtained from both parties. The study was conducted over four consecutive days. On the first day, anthropometric measurements were recorded. On the second, third, and fourth days, athletes' hydration status was assessed before and after training sessions under three different conditions: no intervention, coach encouragement, and educational intervention.

The same training program was applied across all three experimental days. A detailed description of the sessions is presented in Table 1. All training sessions were conducted between 10:00 and 12:00 under consistent environmental conditions (temperature, humidity) throughout the experimental period.

Table 1. Judo training programme for child athletes during the experimental period

Content	Duration (min)
Warm-up	20
"Uchikomi" (Technique repetition; standing, different directions, etc.)	20
Ne-waza workout (groundwork techniques)	20
3 × 4 min "Ne-waza randori" (groundwork battle)	11
6 × 4 min "Tachi-waza Randori"	34
Cool-down	15
Total	120

Note: The same training program was applied across all three intervention days (Day 1, Day 2, and Day 3).

Statistical Analysis

All data analyses were performed using JASP (version 0.19.0) and IBM SPSS Statistics (version 20.0). Descriptive statistics—such as means, standard deviations, and 95% confidence intervals—were calculated for participants' physical characteristics and variables related to the first morning urine samples. Normality was assessed by examining the Shapiro–Wilk test results and evaluating skewness and kurtosis values, with thresholds of ± 2 being considered acceptable. Changes in USG across the three experimental conditions (i) no fluid intake guidance during training, (ii) fluid intake encouraged by the coach, and (iii) pre-training hydration education—were analyzed using a two-way repeated measures ANOVA (2 [time: pre- vs post-training] \times 3 [experimental conditions]). Sphericity was evaluated with Mauchly's test, and where violations occurred, the Greenhouse–Geisser correction was applied to adjust for the degrees of freedom. In cases where significant main or interaction effects were detected, post hoc comparisons were conducted using Holm's adjustment for multiple testing. To determine whether hydration status (classified as hydrated or hypohydrated based on USG thresholds) changed significantly from pre- to post-training, McNemar's test for paired nominal data was subsequently employed, and exact p-values were computed using the exact binomial test. Given the ordinal scale of urine color (UC) scores, changes from pre- to post-training were assessed using the non-parametric Friedman test. When significant differences were observed, Conover's post hoc test with appropriate correction for multiple comparisons was applied. The

significance level was set at $p < 0.05$. Effect sizes were reported as Cohen's d for post hoc comparisons, eta squared (η^2) for ANOVA, and Kendall's W for the Friedman test.

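### Every athlete has the three conditions in one fixed order on consecutive days, so condition cannot be separated from camp day, and the carryover rationale does not protect the education day

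*Combined protocol and SAP*

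**What the plan says.** The aim is causal: "This within-subject experimental study examined the effects of coach encouragement and a brief one-time educational intervention", against a control day without intervention. The Study Design section then gives the layout:

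- Every athlete receives every condition: "each participant underwent all experimental conditions across different days".
- There is one sequence, with one reason given for it: "The order of conditions was fixed (control first, then coach encouragement, and finally education) to minimize potential carryover effects".
- There is no gap between conditions: "The study was conducted over four consecutive days". Day 1 is for anthropometry. On days 2, 3 and 4, "hydration status was assessed before and after training sessions under three different conditions: no intervention, coach encouragement, and educational intervention".
- Some day-to-day differences are controlled. The training programme is the same each day, "All training sessions were conducted between 10:00 and 12:00 under consistent environmental conditions (temperature, humidity) throughout the experimental period", and "Athletes were unaware of the intervention conditions assigned to each day".

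Under Statistical Analysis, changes in urine specific gravity (USG) "were analyzed using a two-way repeated measures ANOVA" with time (pre, post) and condition (three levels) as the factors. A significant main effect or a significant interaction leads to Holm-adjusted post hoc comparisons. No second sequence, parallel control group, repeat control day or washout is described, and neither section lists the aliasing as a limitation.

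**The concern.** With one sequence for everyone, anything that changes over the camp changes together with condition. Fatigue, adaptation and growing familiarity with urine testing are examples. The direction is unknown, so a day effect could imitate a benefit or hide one.

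The carryover rationale is only partly right. Control first keeps that day free of both interventions, and education last keeps education out of the two earlier days. But education directly follows encouragement. If encouragement has a lasting effect, it enters both education contrasts, and education minus control then reflects both interventions.

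The p-values are affected as well as the estimates. The ANOVA error term contains each athlete's own day-to-day variation but not a shift shared by the whole group. To the extent that such shifts exist, the p-values are too small.

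**Working it through.** **Inputs.** The sequence, days, factors and 0.05 level come from the documents. Sample size, residual SD and size of any day effect are not given there, so the plan has no figure to reproduce. Step 1 needs none of these. Steps 2 to 5 assume n = 20, 30 or 40, independent normal residuals with SD 1 and no intervention effect. Day shifts of 0.05, 0.1 or 0.2 are in units of that SD, which is the SD of the pre-to-post change in steps 2 to 4.

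**1. Aliasing.** The model with athlete, time, condition and condition × time has n + 5 columns. Adding day and day × time gives n + 9.

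| n | Columns, rank | With day terms: columns, rank |
|---|---|---|
| 12 | 17, 17 | 21, 17 |
| 20 | 25, 25 | 29, 25 |
| 30 | 35, 35 | 39, 35 |
| 40 | 45, 45 | 49, 45 |

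The rank never rises, so the day terms add no information. For comparison, a model for the pre-to-post change with athlete, condition and day, for 12 athletes, has rank 14 of 16 under the fixed order. Adding carryover leaves it at 14 of 18. With all six orders balanced, the ranks are 16 of 16 and 18 of 18.

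**2. Bias of the contrasts.** A linear drift of d per day in the pre-to-post change biases encouragement − control by d, education − encouragement by d and education − control by 2d. A shift s on the education day alone biases both education contrasts by s and leaves encouragement − control unbiased.

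**3. Interaction test.** The nominal 5% test uses the critical value Fcrit of F with 2 and 2(n − 1) degrees of freedom.

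- Random shared shifts with SD τ: rejection rate = P[F > Fcrit / (1 + nτ²)].
- Linear drift d: noncentral F with noncentrality n(d² + 0 + d²) = 2nd².
- Education-day shift s: noncentrality n(s²/9 + s²/9 + 4s²/9) = (2/3)ns².

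Example: n = 30 and d = 0.2 give 2 × 30 × 0.04 = 2.4, and a rejection rate of 25.2%.

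| Day effect | n | 0.05 | 0.1 | 0.2 |
|---|---|---|---|---|
| Random shared | 20 | 5.7% | 8.0% | 17.9% |
| | 30 | 6.1% | 9.7% | 24.7% |
| | 40 | 6.5% | 11.5% | 30.7% |
| Linear drift | 20 | 5.7% | 7.9% | 17.6% |
| | 30 | 6.1% | 9.5% | 25.2% |
| | 40 | 6.5% | 11.3% | 32.9% |
| Education day only | 20 | 5.2% | 5.9% | 8.9% |
| | 30 | 5.4% | 6.5% | 11.2% |
| | 40 | 5.5% | 7.0% | 13.5% |

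With no shared day effect the rate is 5.0%.

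**4. Holm post hoc contrasts.** These come from 40,000 simulated studies per setting. The plan does not define the post hoc family. The simulation takes three paired t-tests on the pre-to-post change, done only after a significant interaction, with a linear drift of 0.2 per day.

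| n | Encouragement − control | Education − encouragement | Education − control |
|---|---|---|---|
| 20 | 3.8% | 3.7% | 10.2% |
| 30 | 5.6% | 5.5% | 17.0% |
| 40 | 7.6% | 7.2% | 24.6% |

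With no drift each rate is about 1.5%.

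**5. Condition main effect.** Here a random shared day shift moves the USG level equally before and after training. It cancels in the interaction, which stays at about 5%, but not in the condition main effect. In units of the residual SD of the pre/post mean, the random-shift formula of step 3 gives 5.7–6.5% at 0.05, 8.0–11.5% at 0.1 and 17.9–30.7% at 0.2.

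**The case against.** The order is a disclosed choice with a stated reason. The plan claims to minimize carryover, not to eliminate it. Constant programme, clock time and environment, unaware athletes and the pre-training sample all reduce day effects, and the documents report neither a day effect nor carryover. All this is fair: the risk is possible, not demonstrated. These controls still leave open a day-related change in the response to training.

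Pre-training USG might reveal some day shifts. If encouragement is given only during training, the pre-training samples on the control and encouragement days both precede any intervention, and comparing them would show a shift in level. That timing is not stated, and the check cannot detect a day-dependent change from pre to post, so the interaction concern remains.

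The percentages depend on assumed inputs, and the post hoc rates also on an assumed family of comparisons. Correct: they show what could happen and are not evidence about this trial. The case rests on step 1.

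The McNemar test compares pre with post within a day and is not biased by aliasing between days. That stands. The point reaches hydration status and urine colour only where conditions are compared with each other.

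Finally, a remedy in wording might seem to call for a lower severity. But the aliasing affects every contrast that serves the stated aim, and the wording determines what the study can claim.

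**Conclusion.** The concern holds and must be fixed. Condition and camp day are fully aliased at any sample size, and no reanalysis can separate them. The carryover rationale is valid for the control day and for keeping education out of the earlier days, but not for the education day. Whether encouragement persists overnight is unknown, and this design cannot estimate it.

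The practical effect may be negligible or large. Under the assumed inputs, the interaction test's false positive rate runs from 5% with no shared day effect to 33% at a drift of 0.2 residual SD per day with 40 athletes. A difference between days cannot be credited to encouragement alone or to education alone.

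**What to change.** 1. In Study Design, qualify the rationale, for example: *Control first prevents intervention carryover into the control day, and education last prevents education carryover into the earlier days. The education day is not protected from any persisting effect of the previous day's encouragement. Condition and camp day coincide and cannot be separated. The ANOVA p-values assume no shared day effect: on the pre-to-post change for the interaction, and on USG level for the condition main effect.*
2. In Statistical Analysis and in the report, label and interpret the contrasts as day contrasts: encouragement day versus preceding control day; education day, following a day of encouragement, versus control day; education day versus the immediately preceding encouragement day. Do not attribute a difference to one intervention alone.
3. Read the condition main effect in the same way, together with any comparison of urine colour or hydration status across conditions. Pre-to-post tests within a day need no change on this account.

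The cost is in wording and interpretation only, which suits documents written in the past tense. No new sessions or data are needed. The price is a weaker causal claim.

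### Does the 11-minute entry for three 4-minute groundwork bouts in Table 1 undermine the standardised training session?

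*Combined protocol and SAP*

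**What the plan says.** The Study Design section describes a four-day camp. Body measurements are taken on the first day, and hydration is assessed before and after training "On the second, third, and fourth days", with one condition per day in a fixed order. The session is meant to be the same each time, and its timing is stated: "All training sessions were conducted between 10:00 and 12:00 under consistent environmental conditions".

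Table 1 breaks the session into six blocks with a duration for each and a total of 120 minutes. The row in question is labelled "3 × 4 min 'Ne-waza randori' (groundwork battle"), and its entry reads "groundwork battle) 11". The only other row built from timed bouts is "6 × 4 min 'Tachi-waza Randori' 34". The note under the table states: "The same training program was applied across all three intervention days (Day 1, Day 2, and Day 3").

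The documents state no rest interval for either sparring block.

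**The concern.** Three bouts of 4 minutes cannot fit into 11 minutes. The table is the only specification of the exercise load, and that load affects how far urine specific gravity (USG) moves from before to after training. Rest between bouts also determines how much chance there is to drink.

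The design makes this more sensitive than usual. The order of conditions is fixed and each condition occupies a single day, so condition and day cannot be separated. If the coach had to cut a bout short or run past 12:00, and did so differently on different days, the difference would be attributed to a condition. The day numbers in the table note (1 to 3) also seem at first to disagree with the text, where the conditions fall on days 2 to 4.

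**Working it through.** **Inputs, all from Table 1 (minutes):** warm-up 20, uchikomi 20, groundwork techniques 20, groundwork sparring 11, standing sparring 34, cool-down 15, stated total 120.

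**The plan's own total.** 20 + 20 + 20 + 11 + 34 + 15 = 120. This reproduces the stated total and equals the window from 10:00 to 12:00. Because the sum works only with 11, that digit is unlikely to be a fault in reading the PDF. The digits in the bout label have no such cross-check.

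**Label against duration.**
- Groundwork sparring: 3 × 4 = 12 minutes of bouts against 11 listed, a shortfall of 1 minute, or 1/120 = 0.8% of the session.
- Standing sparring: 6 × 4 = 24 minutes of bouts against 34 listed, leaving 34 − 24 = 10 minutes.

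**If the label is taken as given and the duration is changed.** There are two gaps between three bouts. With an assumed rest of r minutes per gap, the block is 12 + 2r and the session is 120 − 11 + 12 + 2r.

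| Assumed rest per gap (min) | Block (min) | Session (min) |
|---|---|---|
| 0 | 12 | 121 |
| 1 | 14 | 123 |
| 2 | 16 | 125 |

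The 2-minute row borrows from the standing block, where 10 spare minutes over 5 gaps is 2 minutes each. That is an inference from a different activity. Only the 1-minute discrepancy comes from the documents.

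**If the duration is taken as given.** The bouts would average 11/3 = 3.67 minutes with no rest, or (11 − 2)/3 = 3.0 minutes with an assumed 1-minute rest in each gap. The session then stays at 120 minutes with no overrun. These figures only show that such readings exist; they do not indicate which entry is right.

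**Day numbers.** The note counts the three intervention days, and the text counts the four days of the camp. Intervention days 1, 2 and 3 are camp days 2, 3 and 4. The two counts agree.

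**Use in the analysis.** The Statistical Analysis section specifies a two-way repeated measures ANOVA of USG (2 times × 3 conditions), McNemar's test for hydration category and the Friedman test for urine colour. None of them takes block or session duration as an input. All rest on what was measured before and after the sessions that were actually run, however the table labels them.

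**The case for a change.** The strongest case for acting is that Table 1 is the sole account of an exercise load that must be equal across conditions, in a design where each condition is a single day. A reader cannot tell how many minutes of groundwork sparring took place or how much rest came between bouts, and the correction would cost one table row.

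Part of this stands. The contradiction is real, and anyone wishing to repeat the session exactly would have to ask which entry is right.

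The threat to the comparison does not stand. The documents state in both the text and the table note that the programme was the same on all three days, and nothing in them suggests a day on which it differed. A misprint in one shared table applies equally to all conditions. Confounding of condition with day is a feature of the fixed order and would remain, whatever this row said. Correcting the row would also give no evidence on whether the sessions matched from day to day, because one table describes all three.

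It also goes too far to say that the session could not be run. The total adds up, and an overrun follows only if the block duration, rather than the bout label, is the wrong entry.

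**Conclusion.** The row is internally inconsistent by 1 minute (12 against 11, or 0.8% of 120), and the documents do not show whether the bout count, the bout length or the block duration is at fault. The 120-minute total comes into question only if the block duration does. Any larger figure, such as 125 minutes, depends on an assumed rest interval. The day numbering is not an error.

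This is a clerical slip in the description of sessions already conducted. The label and the duration need to be reconciled from the session record if the table is reproduced, but that bears on replication alone. No change to the design or the analysis follows, because the discrepancy is shared by all three conditions and no planned test uses the duration. This conclusion relies on the documents' statement that the same programme was applied on each day. If session records showed that the days differed, that would be a separate problem, and editing this row would not solve it.

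### If any USG sample is missing, the planned 2 × 3 repeated-measures ANOVA also discards that athlete's intact days; a mixed model on same-day changes would keep them

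*Combined protocol and SAP*

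**What the plan says.** Under Study Design, athletes' "hydration status was assessed before and after training sessions under three different conditions". Two samples on each of three days make six USG values per athlete. The same section says that "each participant underwent all experimental conditions across different days".

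Under Statistical Analysis, USG changes "were analyzed using a two-way repeated measures ANOVA", with time (two levels) and condition (three levels) both within athlete. On the covariance, "Sphericity was evaluated with Mauchly's test, and where violations occurred, the Greenhouse–Geisser correction was applied". Where a main effect or the interaction is significant, Holm-adjusted post hoc comparisons follow.

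Neither section says what happens to an athlete with fewer than six values, how many samples were missing, or that none were. No sample size, SD, correlation or expected missing rate is given.

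**The concern.** The study question is answered by two contrasts: coach encouragement against control, and education against control, each in the pre-to-post change. A classical repeated-measures ANOVA uses only athletes with every cell filled. This is how the method works; the documents do not spell it out. A child who lacks, say, one post-training sample on the coach day is removed from the education–control contrast too, although both of those days are complete.

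If isolated samples are missing, the two contrasts therefore rest on fewer athletes than the collected data allow, with wider intervals and lower power. Dropping incomplete athletes also generally needs the loss to be missing completely at random, which is a stronger condition than a likelihood-based model needs.

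**Working it through.** **Inputs.** From the documents: six samples per athlete, the 2 × 3 ANOVA, and the 0.05 significance level. Everything else is assumed: per-sample missing rate q, n = 30, change SD 1, correlation of changes across days 0.3, and a true education–control difference of 0.7. There is no figure in the plan to reproduce.

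**Step 1: the unit of analysis.** In a complete simulated data set (n = 20), the time-by-condition test of the 2 × 3 ANOVA gave F = 5.329 on 2 and 38 df. A one-way repeated-measures ANOVA on the three same-day changes (post minus pre) gave the same F and df. The same-day change is therefore the right unit. With one cell removed, the ANOVA routine rejected the data as unbalanced.

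**Step 2: what the alternative reproduces.** On those complete data, a REML model with unstructured 3 × 3 covariance on the changes gave coach–control −0.3109 (SE 0.3263) and education–control −0.9044 (SE 0.3112), identical to the paired contrasts. The omnibus statistic did not match: Wald/2 was 7.71 (Hotelling F 7.30) against the ANOVA F of 5.33.

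**Step 3: share lost under independent loss.** Athletes dropped = 1 − (1 − q)^6. Same-day changes unavailable = 1 − (1 − q)^2.

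| q | Athletes dropped | Changes unavailable |
|---|---|---|
| 2% | 11.4% | 4.0% |
| 5% | 26.5% | 9.8% |
| 10% | 46.9% | 19.0% |

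**Step 4: precision and power.** 10,000 runs per cell, two-sided 5% for one contrast before Holm, Kenward–Roger df, complete case vs model.

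| q | SD of contrast | Power |
|---|---|---|
| 0 | 0.217 vs 0.217 | 87.7% vs 87.7% |
| 2% | 0.231 vs 0.224 | 83.6% vs 86.5% |
| 5% | 0.255 vs 0.231 | 75.6% vs 83.6% |
| 10% | 0.300 vs 0.250 | 59.2% vs 77.4% |

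Hand check of the complete-case SD: √(2 × (1 − 0.3)/30) = 0.216 with none missing. At q = 5%, 30 × 0.735 = 22.05 athletes remain, and √(1.4/22.05) = 0.252. Separate runs with the same n and correlation gave 0.251 to 0.254 vs 0.233 to 0.234 at 5%. Type I error stayed within 4.6–5.3% (complete case) and 4.6–5.4% (model).

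**Step 5: the pattern of loss matters.** Each row has 5% of samples missing.

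| Pattern | Athletes dropped | Power | Variance ratio |
|---|---|---|---|
| Independent samples | 26% | 75.6% vs 83.6% | 1.22 |
| Whole days | 14% | 81.8% vs 85.5% | 1.10 |
| Same athletes lack every post sample | 10% | 83.1% vs 83.1% | 1.00 |
| Whole athletes | 5% | 86.4% vs 86.4% | 1.00 |

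One, three or five isolated missing samples in 30 athletes give 87.2% vs 87.9%, 83.1% vs 85.5%, and 80.6% vs 85.2%.

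**Step 6: other assumptions, at 5% independent loss.** Change correlation 0: 60.1% vs 70.0%. Correlation 0.5: 87.7% vs 93.0%. n = 20: 55.3% vs 64.1%. n = 50: 93.4% vs 97.1%.

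**The case against.** The strongest reply is that the trigger is not in the documents. The study is reported in the past tense, ran over consecutive days of one camp, and states that every athlete went through every condition. That points towards completeness. It stands as far as it goes: it makes a missed day unlikely, but it does not establish that all six samples were obtained. A reader might infer from this point that athletes were in fact dropped or power lost. The documents do not support that.

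Second, all the sizes are assumed, and independent loss is the pattern most favourable to the model. This stands; step 5 shows the gain falling to zero.

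Third, the comparator is one unadjusted paired contrast, not the full planned sequence of omnibus tests followed by Holm-adjusted comparisons. The power figures are therefore not the plan's power. A reader might also infer from the complete-data equality that the model could replace the ANOVA without consequence. It could not: the equality covers the paired contrasts only, not the omnibus interaction test or post hoc tests with a pooled error term. This is why the ANOVA should stay when the data are complete.

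Fourth, a simpler remedy recovers part of the loss: a paired test on every athlete with both relevant days. Under the same assumptions (40,000 runs) its power was 85.0%, 79.9% and 69.8% at 2%, 5% and 10%, against 83.3%, 75.0% and 59.2% for complete cases. That is a little over half of the gain. The mixed model obtains the rest by using the third day.

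**Conclusion.** The point holds as a conditional, low-cost improvement, not as a demonstrated error. The planned ANOVA can use only athletes with all six values, and the plan neither covers an incomplete set nor says there was none. No data are shown to be lost, and there is no avoidable loss if all samples were obtained or if losses fall on whole athletes.

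With isolated missing samples the gain is mainly precision. In the illustration (n = 30, correlation 0.3, 5% independent loss) the contrast SD falls from 0.255 to 0.231 and power rises by 8 points (83.6% − 75.6%). For a single missing sample the difference is under one point. It would be too strong to call the gain purely one of precision, because the model is valid under missing at random whereas dropping athletes generally needs missing completely at random. It would also be too strong to say that the model cures bias. With 10% of samples missing, all taken from the highest post-training USG, a true −0.70 was estimated as −0.66 (complete case) and −0.65 (model) at correlation 0.3, and as −0.63 by both at correlation 0.

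**What to change.** State the number of samples missing by condition and time, and the number of athletes in each analysis. Then:

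- **If none is missing:** keep the planned ANOVA with its omnibus interaction test, and say that the data were complete.
- **If any is missing:** estimate the coach–control and education–control differences in same-day change (post minus pre USG) with a REML mixed model. Use condition as fixed effect, an unstructured 3 × 3 within-athlete covariance, and Kenward–Roger or Satterthwaite df. Report both with 95% CIs and Holm adjustment, with the complete-case ANOVA as a sensitivity analysis.

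The unstructured covariance lets the three changes differ in variance and correlate freely, so for these contrasts it covers the non-sphericity that the plan handles with Mauchly's test and Greenhouse–Geisser. Random effects for athlete and athlete-day alone do not. With complete data and n = 30 they gave type I error of 2.1% at change correlation 0.3 and 0.7% at 0.5. With change variances of 1.5/0.5/1.5 by condition and correlation 0 it was 8.0%.

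The cost is SAP wording and a re-analysis of existing data. The downsides should be stated: a missing-at-random assumption, six covariance parameters in what may be a small sample, days with only one sample unused, and a condition main effect that stays with the ANOVA. The change does not repair loss that depends on unseen USG, does not address the McNemar or Friedman analyses, and does not separate condition from day under the fixed order.

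### The urine-colour analysis, as worded, states no test of whether the pre-to-post change differs between control, encouragement and education

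*Combined protocol and SAP*

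**What the plan says.** The Study Design section sets the question: "This within-subject experimental study examined the effects of coach encouragement and a brief one-time educational intervention", each against a no-intervention control. Hydration is measured before and after training on three days, one per condition, so each athlete contributes 2 × 3 = 6 values. The order is not randomised: "The order of conditions was fixed (control first, then coach encouragement, and finally education".

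The Statistical Analysis section treats the two urine measures differently.

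- **USG.** The sentence opens with "Changes in USG across the three experimental conditions", lists the three conditions and specifies a 2 × 3 repeated measures ANOVA. Follow-up is explicit: "In cases where significant main or interaction effects were detected, post hoc comparisons were conducted using Holm's adjustment for multiple testing".
- **UC.** "Given the ordinal scale of urine color (UC) scores, changes from pre- to post-training were assessed using the non-parametric Friedman test". Then: "When significant differences were observed, Conover's post hoc test with appropriate correction for multiple comparisons was applied". Kendall's W is the effect size. Neither the ranked levels nor the correction is named, and no condition factor appears.

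**The concern.** The time-by-condition interaction for USG tests whether the change over training depends on condition, which is what the study asks. Friedman has a single within-athlete factor, so it has no interaction term, and what it tests depends entirely on which columns are ranked. The UC text leaves that open.

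If the test is pre against post within each condition, UC can be brought to bear on the interventions only by setting a significant result on one day beside a non-significant result on another. That does not test a difference. If all six cells are ranked, a significant omnibus result or a large W may reflect nothing more than training itself, and a post-against-post pair can differ because the days started at different levels. In either case UC could be reported as supporting an intervention effect that was never tested.

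**Working it through.** The plan states no sample size, UC variance or power, so there is no figure of its own to reproduce. The check is first algebraic, then illustrative.

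**Algebra.** For n athletes and k ranked levels, with within-athlete ranks r and column rank sums R_j, the tie-corrected Friedman statistic is

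Q = (k − 1) Σ_j [R_j − n(k + 1)/2]² / [Σ r² − nk(k + 1)²/4], referred to χ² on k − 1 df.

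(a) *k = 2, pre and post in one condition.* With n₊ athletes rising and no ties, the numerator is 2(n₊ − n/2)² and the denominator is 5n − 4.5n = 0.5n. So Q = (2n₊ − n)²/n, the uncorrected sign-test chi-square. On one simulated set of n = 20, both gave p = 0.6547 (an 11–9 split: 2²/20 = 0.20). No condition enters.

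(b) *k = 6, all cells.* The null hypothesis is that all six cells are alike. A time effect common to the three conditions violates it, as does a day effect with no difference in change. Conover then has 6 × 5/2 = 15 pairs, each comparing two cells. None compares two changes.

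(c) *k = 3, post minus pre for each condition.* A common time effect or a level shift between days cancels in the difference (apart from rounding and the ends of the scale). This version asks the study question.

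**Illustration.** All inputs are assumed: latent normal scores rounded and clipped to a 1–8 scale, mean 3.5, SD 1.3, within-athlete correlation 0.5, α = 0.05, 10,000 trials per setting. Columns give n = 20/30/40.

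| Same change in all three conditions | Shift 0.3 SD | Shift 0.5 SD |
|---|---|---|
| (a) control day significant, at least one intervention day not | 18.5/27.8/33.0% | 35.0/36.9/31.0% |
| (b) six-cell omnibus significant | 29.7/46.8/60.7% | 74.6/92.8/98.3% |
| (b) any same-time pair between conditions flagged (Conover, Holm over 15) | 2.0/2.1/2.2% | 2.3/3.0/2.9% |
| (c) Friedman on three changes | 4.9/5.0/5.0% | 4.8/4.9/4.5% |

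With correlation between 0.3 and 0.7, row (a) ranges over 12–39%.

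*Adding day-level drift.* Keep the 0.3 SD change equal in all conditions, but lower both pre and post by 0.25 SD on the encouragement day and 0.5 SD on the education day. Latent post-training colour then differs between control and education by 0.5 × 1.3 = 0.65 points, while the change is 0.3 × 1.3 = 0.39 points on every day. The control-post against education-post pair is flagged in 19.9/35.3/50.3% of trials. Friedman on post-training values alone rejects in 38.3/55.9/68.7%. Friedman on three changes stays at 4.6/5.1/4.6%.

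*A second set of assumptions.* With between-athlete SD 1.0, within-athlete SD 0.8, a 1-point rise in every condition, n = 15 to 40 and 2,000 trials, the six-cell test rejected in 99–100% and the change-score test in 4.5–5.2%. With a condition main effect only (0/−0.5/−1 point), the six-cell test rejected in 92–100% although the change was equal.

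**The case against.** The best counter-argument is that the intended analysis may already be (c). The UC sentence says that changes were analysed; the USG sentence ties the same word to the three conditions; and a Conover step with a multiplicity correction is pointless with two levels. This makes (a) a poor fit as the sole analysis, and the documents do not show that no between-condition test was run. But Conover fits six cells as well as three changes. The adjacent McNemar sentence also uses pre-to-post wording for a plain before/after comparison without naming a condition. So (c) is possible but not stated.

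Four further points have weight.

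- The six-cell rates are power for a real time effect, not false positives, and without drift a same-time pair between conditions is flagged in only 2–3%. The 20–50% figure depends on an assumed drift, under which post-training levels really do differ; the error lies in reading that as a different change.
- The criterion in row (a) is loose. Requiring both intervention days to be non-significant gives about 13/14/15% at 0.3 SD and 13/9/4% at 0.5 SD. The plan also does not say it would interpret results that way.
- USG already addresses the core question, and neither measure is designated primary.
- The McNemar analysis of hydration status has the same silence about conditions, so UC is not alone. That widens the gap rather than excusing it.

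**Conclusion.** The concern holds as a statement about the wording: no UC test of a difference in change between conditions is specified, and two of the three available readings would not supply one. The logical part needs no assumptions. The percentages do: scale, SD, correlation, n, shift and drift are all assumed, and the two sets of assumptions put the six-cell rejection rate under equal change anywhere from 30% to 100%. They illustrate a mechanism and do not size an error in this trial. What is stable across every setting is that the change-score version stays near 5% when the changes are equal.

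This should be corrected, but it is not fatal, because USG has an interaction test. Confidence is medium, because the change-score reading may have been intended. The unnamed Conover correction is a smaller reporting gap in the same sentence.

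**What to change.** State the UC layout in the Statistical Analysis section:

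- Friedman across the three conditions on each athlete's post-minus-pre UC, with Kendall's W taken from that test.
- Three Conover comparisons, with Holm named as the correction to match USG.
- Post-training UC across conditions as a sensitivity analysis only, because it picks up day-level drift.
- Wilcoxon signed-rank tests within a condition as description only.
- Any significant result reported as a difference between condition-days. The fixed order confounds condition with day, and this change does not remove that.

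The cost is a wording change and a re-run in the same software on data already collected. There are two drawbacks. Differencing treats steps on an ordinal scale as comparable; an ordinal mixed model with a time-by-condition term is an alternative. Power is also modest: for true changes of +0.5/+0.25/0 SD under the main assumptions it is 20.2/29.8/38.5% at n = 20/30/40, against 37.8/55.9/69.8% for post-only UC. That advantage holds only if the days start level: with drift and equal changes, post-only UC rejected almost as often (38.3/55.9/68.7%). Under the second set of assumptions, with changes of +1/+0.5/0 points, change-score power is about 55/73/85% at the same n. A null UC result should therefore not be read as no effect.
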